7. Correlation and regression analysis of PIF and/or Inhalations events at varying thresholds
 - a. Daily PIF 10, 20, 30 or 40% below Baseline PIF
 - b. Daily Inhalations at 2, 4 or 6 Inhalations above Baseline Inhalations
 - c. Daily PIF and/or Inhalations duration of 2, 3 or 4 or more days outside of Baseline
8. Frequency and duration of AEC events of 2 or more major symptoms (Type I and Type II)
9. Frequency and duration of BCSS events (increase in BCSS by 2 above Baseline BCSS)
10. Correlation and regression analysis of PIF, Inhalations and IV events with AEC events
11. Correlation and regression analysis of PIF, Inhalations and IV events with BCSS event
12. Correlation of Digihaler changes in PIF above baseline and changes in CAT
13. Correlation off changes in SABA use above baseline with changes in CAT
14. Correlation of Digihaler changes in Inhalation Volume above baseline with changes in CAT
15. Descriptive sub-group analysis of PIF, Inhalations and IV thresholds by FEV1 severity, GOLD groups and BODE at Baseline.

REFERENCES

1. World Health Organization. Global Health Estimates 2016: Deaths by Cause, Age, Sex, by Country and by Region 2000–2016. 2018 [accessed October 2020]. s
2. GOLD. Global Strategy for the Diagnosis, Management, and Prevention of Chronic Obstructive Pulmonary Disease. 2020 Report. www.goldcopd.org.
3. Nici L, et al. Pharmacologic Management of Chronic Obstructive Pulmonary Disease. An Official American Thoracic Society Clinical Practice Guideline Am J Respir Crit Care Med. 2020; 201:56-59.
7. van der Molen T, Miravitles M, Kocks JW. COPD management: role of symptom assessment in routine clinical practice. Int J Chron Obstruct Pulmon Dis. 2013; 8:461-471.

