The number of albuterol rescue inhalations used and measured over 2 weeks at baseline using the Digihaler device. Baseline inhalations per day at baseline will be derived by the total number of inhalations divided by the total number of days during the baseline period and reported as inhalations per day or Baseline Inhalations/day.
3. Baseline Inhalation Volume (**Baseline IV**) measured via Digihaler device
IV is the volume of air inhaled during an albuterol rescue inhalation effort, expressed in Liters. Individual IV measurements collected over 2 weeks at baseline will be measured using the Digihaler device. The mean value for IV during the baseline period will be reported as the Baseline IV.

Protocol Overview

The trial is an unblinded open label single center study designed to identify trends in Peak Inspiratory Flow (PIF) rates and Rescue Albuterol Inhaler usage (Inhalations) that associate with disease deterioration as defined by worsening of symptoms and reduced lung function in patients with COPD.

The study will consist of a run-in period of approximately 2 weeks, a treatment period of 6 months and a follow-up period of 1 week. Twenty (20) patients with COPD requiring intermittent short acting beta agonist (SABA) rescue inhaler usage, but not requiring frequent SABA nebulizer rescue usage, will be enrolled.

After signing informed consent, patients will undergo a screening evaluation. During the run-in period, patients will continue on their COPD maintenance treatments, while discontinuing all previously prescribed periodic use rescue medications. Upon completion of screening, all patients will be dispensed a ProAir Digihaler to be used exclusively as their rescue medication throughout the duration of the study. During the run-in period all rescue inhaler usage will be electronically monitored and patient data from the Digihaler Dashboard will be downloaded every other business day basis (Monday, Wednesday and Friday).

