All patients with Daily Inhalations exceeding Baseline Inhalations by ≥ 4 Inhalations per day and/or with a Daily PIF $\leq 80\%$ of Baseline PIF for 2 consecutive days will be DEFINED as “at risk”. For each “at risk” event, the patient will be contacted, their health status reviewed, and CAT and Anthonisen Exacerbation questionnaires will be administered. Based on symptoms, patients may also be advised to seek additional medical care.

All patients will be contacted on a monthly basis, irrespective of “risk” findings and seen in person every 3 months. All medication usage (including ProAir Digihaler medication usage), changes in medical care, healthcare contacts and usage, and any adverse events will be recorded. All office records for the intervening time period will be reviewed and Information for any non-office healthcare contacts and usage will be requested to provide detailed clinical information for comparison to Digihaler usage records.

At months 3 and 6 on treatment, all subjects will return to the research center, where vital signs, Anthonisen Exacerbation and CAT questionnaires, and post bronchodilator spirometry will be assessed. All medication usage (including ProAir Digihaler medication usage), changes in medical care, healthcare contacts and usage, and any adverse events will be recorded. All office records for the intervening time period will be reviewed and Information for any non-office healthcare contacts and usage will be requested to provide detailed clinical information for comparison to Digihaler usage records. Three (3) new ProAir Dihgihalers will be dispensed at month 3.

Throughout the treatment period, all rescue inhaler usage will be electronically monitored and downloaded from the Digihaler Dashboard by the research center on an every other business day basis (Monday, Wednesday and Friday). At the completion of each Digihaler Dashboard Data Download, comparisons of Daily PIF (average PIF of all rescue inhalations in a day) and Daily Inhalations (number of rescue inhalations in a day) to Baseline PIF and Baseline Inhalations will be made.

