All patients with Daily Inhalations exceeding Baseline Inhalations by ≥ 4 Inhalations per day and/or with a Daily PIF $\leq 80\%$ of Baseline PIF for 2 consecutive days will be DEFINED as “at risk”. For each “at risk” event, the patient will be contacted, their health status reviewed, and CAT and Anthonisen Exacerbation questionnaires will be administered. Based on symptoms, patients may also be advised to seek additional medical care.

At the conclusion of the 6-month treatment period the patients will return to the research center for a final visit, returning all study medication not previously returned. The patient will be advised to resume usage of their prior rescue inhaler medication at that time. A telephone call will be made to the patient 1 week after their final in-person visit, to assess vital status and any adverse events that may have occurred subsequent to discontinuing the ProAir Digihaler.

- All study information, including study app login information, will be labeled with a subject code number and will not include subject name, initials, address, telephone number or e-mail address.
- A secured master spreadsheet will provide the link between required subject identification information and the subject code number.
- The link between subject identification information and subject code number will not be shared.
- All data provided to Teva will only be transmitted using the subject code number.

Visit Schedule

Screening visit (V1):

- Review and sign consent
- Obtain demographic and medical history, including exacerbation and past medical history
- Obtain smoking status and history
- Review all current medications, including all rescue therapies
- Review safety issues, device issues and adverse events
- Review inclusion and exclusion criteria
- Obtain vital signs, including BMI
- Perform Pregnancy test (if of child-bearing potential)
- Complete physical examination
- Complete Health Questionnaires [CAT, mMRC, Anthonisen Exacerbation criteria and BCSS]

- Dispense ProAir Digihaler and establish smartphone connectivity and internet access to the Digihaler Dashboard
- Instruction and training in the proper use of the ProAir Digihaler
- Provide paper copies of CAT, BCSS and Anthonisen Exacerbation criteria, to be completed at home on a weekly basis, along with instructions and stamped envelopes for questionnaire return upon completing
- Instructions for pre-spirometry medication washout prior to visit 2

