- Schedule visit 2 for approximately 14 +/- 3 days after visit 1

Run-in visit (V2):

- Review medications, including all rescue therapies and medication washout
- Review safety issues, device issues and adverse events
- Review inclusion and exclusion criteria
- If medication washout has not occurred, reschedule v2 within 1 week
- If medication washout has occurred, complete health questionnaires [CAT, mMRC, Anthonisen Exacerbation criteria and BCSS]
- Perform Pregnancy test (if of child-bearing potential)
- Review and compare health history during the run-in period, returned paper questionnaires and visit 2 health questionnaires to screening medical information and questionnaires to ensure stable baseline clinical condition
- Download Digihaler Dashboard Data and determine if the minimum number of rescue inhalations required during run-in have occurred
- If clinical conditions are not stable or if inadequate numbers of inhalations have occurred during run-in, re-schedule v2 for 2 weeks later
- If clinical conditions remain unstable or inadequate inhalations occur during the extended run-in, withdraw patient from the study
- If medication washout, clinical stability and adequate rescue inhalation criteria during run-in have been met, perform vital signs
- Perform pre-bronchodilator Inspiratory Capacity (see testing)
- Perform pre-bronchodilator Spirometry (see testing),
- Administer 4 inhalations of albuterol via the ProAir Digihaler
- Perform post-bronchodilator Inspiratory Capacity (see testing)
- Perform post-bronchodilator Spirometry 20-30 minutes after albuterol dosing (see testing)
- If post-bronchodilator spirometry entry criteria are not met (inclusion criteria), withdraw subject from the study
- If post-bronchodilator study spirometry criteria are met, instruct patient to self-administer their maintenance COPD medications
- Perform 6-minute walk testing 1 hour after maintenance medication administration

- Based on spirometry, CAT, and 6-minute walk results, determine GOLD group, airflow/FEV₁ severity and BODE score
- Dispense 2 additional ProAir DigiHalers and establish smartphone connectivity and internet access to the DigiHaler Dashboard
- Instruction and training in the proper use of the ProAir DigiHaler
- Provide paper copies of CAT, BCSS and Anthonisen Exacerbation criteria, to be completed at home on a weekly basis, along with instructions and stamped envelopes for questionnaire return upon completing

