- Instruct patient to continue use of all maintenance medications and to use the ProAir DigiHaler as their rescue inhaler as needed
- Schedule month 1 and 2 telephone contacts
- Schedule in-clinic visit 3 for approximately 3months from v2

3-month follow-up (visit 3)

- Review medications, including all rescue therapies and medication washout
- Review safety issues, device issues and adverse events
- Perform Pregnancy test (if of child-bearing potential)
- Complete health questionnaires [CAT, mMRC, Anthonisen Exacerbation criteria and BCSS]
- Download DigiHaler Dashboard Data
- Recover the 3 dispensed ProAir DigiHalers
- Review any changes in health history, health care contacts, changes in medications and any healthcare utilization
- Review paper questionnaires submitted over the prior 3 months and any clinic or other healthcare records
- Perform vital signs
- Determine timing of maintenance medication usage that morning will be recorded
- Administer 4 inhalations of albuterol via the ProAir DigiHaler
- Perform post-bronchodilator Inspiratory Capacity (see testing)
- Perform post-bronchodilator Spirometry 20-30 minutes after albuterol dosing (see testing)
- Dispense 3 additional ProAir DigiHalers and establish smartphone connectivity and internet access to the DigiHaler Dashboard
- Instruction and training in the proper use of the ProAir DigiHaler
- Provide paper copies of CAT, BCSS and Anthonisen Exacerbation criteria, to be completed at home on a weekly basis, along with instructions and stamped envelopes for questionnaire return upon completing
- Instruct patient to continue use of all maintenance medications and to use the ProAir DigiHaler as their rescue inhaler as needed

- Schedule month 4 and 5 telephone contacts
- Schedule in-clinic visit 4 for approximately 3months from v3

6-month follow-up (visit 4)

- Review medications, including all rescue therapies and medication washout
- Review safety issues, device issues and adverse events
- Perform Pregnancy test (if of child-bearing potential)
- Complete health questionnaires [CAT, mMRC, Anthonisen Exacerbation criteria and BCSS]
- Download Digihaler Dashboard Data
- Recover the 3 dispensed ProAir Digihalers
- Review any changes in health history, health care contacts, changes in medications and any healthcare utilization
- Review paper questionnaires submitted over the prior 3 months and any clinic or other healthcare records
- Perform vital signs

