- Determine timing of maintenance medication usage that morning will be recorded
- Administer 4 inhalations of albuterol via the ProAir Digihaler
- Perform post-bronchodilator Inspiratory Capacity (see testing)
- Perform post-bronchodilator Spirometry 20-30 minutes after albuterol dosing (see testing)
- Dispense 3 additional ProAir Digihalers and establish smartphone connectivity and internet access to the Digihaler Dashboard
- Instruction and training in the proper use of the ProAir Digihaler
- Provide paper copies of CAT, BCSS and Anthonisen Exacerbation criteria, to be completed at home on a weekly basis, along with instructions and stamped envelopes for questionnaire return upon completing
- Instruct patient to continue use of all maintenance medications
- Instruct patient to resume use of the original rescue inhaler(s) as needed
- Schedule 1-week safety telephone contacts

Months 1, 2, 4 and 5 Telephone Contact:

- Contact patient at scheduled date and time by telephone
- Review changes in health history, health care contacts, changes in medications, any healthcare utilization and any safety issues
- Review paper questionnaires submitted over the prior month
- Download Digihaler Dashboard Data
- Provide reminders and instructions, as needed.

Safety Telephone contact:

- Contact patients at scheduled date and time by telephone 1-week after visit 4
- Review patient health status and any safety issues that may have occurred after discontinuation of study medication

Testing

CAT questionnaire: (see appendix) will be self-administered at home on a weekly basis and at all clinic visits.

Anthonisen Exacerbation Criteria (AEC): (see appendix) will be self-administered at home on a weekly basis and at all clinic visits.

BCSS questionnaire: (see appendix) will be self-administered at home on a weekly basis and at all clinic visits.

mMRC questionnaire: (see appendix) will be self-administered at clinic visits 1 and 2.

Vitals signs, BMI, History, Physical Examination will be performed as per clinical standards.

Medication washout: Medication washout will occur prior to visit 2 as per the following:

SABA – 6 hours
SAMA – 6 hours
BID LABA or LABA/ICS – 12 hours
BID LAMA – 12 hours
BID LABA/LAMA/ICS – 12 hours
QD LABA or LABA/ICS – 24 hours
QD LAMA – 24 hours
QD LABA/LAMA/ICS – 24 hours

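### Post-bronchodilator FEV1 is measured after an enforced maintenance-drug hold at visit 2 but with uncontrolled maintenance dosing at visits 3 and 4, so change in FEV1 may be shifted toward improvement by an unknown amount

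*Protocol*

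**What the plan says.** **Before and at visit 2.** In the Protocol Overview, "During the run-in period, patients will continue on their COPD maintenance treatments", so patients reach visit 2 on treatment. The screening visit list includes "Instructions for pre-spirometry medication washout prior to visit 2". The Testing section names that visit alone, "Medication washout will occur prior to visit 2 as per the following", and sets the hours: 6 h for short-acting drugs, 12 h for twice-daily and 24 h for once-daily long-acting drugs. The visit 2 list enforces them: "If medication washout has not occurred, reschedule v2 within 1 week". Spirometry follows, before and after four albuterol inhalations, and the maintenance dose comes last: "If post-bronchodilator study spirometry criteria are met, instruct patient to self-administer their maintenance COPD medications".

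**Before and at visits 3 and 4.** Patients leave visit 2, and again visit 3, with this instruction: "Instruct patient to continue use of all maintenance medications and to use the ProAir DigiHaler as their rescue inhaler as needed". No hold is instructed. On the test morning the list says "Determine timing of maintenance medication usage that morning will be recorded". Four albuterol inhalations and post-bronchodilator spirometry then follow. Both visit lists also include medication washout in the medication review, with no hours and no action if washout did not happen. The Protocol Overview for months 3 and 6 says only that "Anthonisen Exacerbation and CAT questionnaires, and post bronchodilator spirometry will be assessed", along with vital signs, and mentions no washout.

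**Use of the measurement.** Change in FEV1 is listed as a secondary outcome, both in the outcome list and under Statistical Analysis. Under Testing, Spirometry, the pre-dose test belongs to visit 2 alone and the post-dose test to visits 2, 3 and 4.

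**The concern.** A change score reads as disease change only if both ends are measured under like conditions. Here the visit 2 value is taken about one dosing interval after the last maintenance dose. The visit 3 and 4 values may be taken a few hours after a fresh one. If a fresh long-acting dose adds anything to FEV1 beyond four albuterol inhalations, the follow-up value is raised relative to baseline. The shift would then be toward improvement, the direction that could hide a decline in a study looking for deterioration.

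The washout line at visits 3 and 4 makes this worse in practice. The Testing section limits washout to visit 2, yet site staff are asked to review it at two later visits. They cannot tell from the document whether patients should hold the morning dose, so practice may differ between patients.

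**Working it through.** **1. Compare the visits.**

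| Feature | Visit 2 | Visits 3 and 4 |
|---|---|---|
| Maintenance treatment in the preceding weeks | Continued | Continued |
| Hold instructed beforehand | Yes, at screening | No |
| Hours fixed | 12 h or 24 h | None |
| Action if not held | Reschedule | None |
| Maintenance dose that day | After post-dose test | Not controlled; time recorded |
| Albuterol before post-dose test | 4 inhalations | 4 inhalations |
| Pre-dose spirometry | Yes | No |
| Post-dose spirometry | Yes | Yes |

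The albuterol step is matched and the maintenance-drug state is not. Visit 2 is the only spirometry listed before the treatment period, so it is the natural baseline for change in FEV1.

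**2. Size.** The protocol gives no SD, effect size or power, so there is no figure of its own to reproduce. What follows is an illustration.

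Inputs:
- n = 20, from the Protocol Overview.
- d, the increment of a fresh maintenance dose over four albuterol inhalations: assumed 0 to 0.10 L.
- p, the share of patients who are on a long-acting drug and dose before the visit 3 or 4 test: assumed 0 to 1.
- SD0, the SD of paired change in FEV1 without this effect: assumed 0.15 to 0.25 L.

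Formulas:
- Mean bias = d × p
- SD² = SD0² + d² × p × (1 − p)
- SE = SD / √20
- Coverage of a nominal 95% t interval for mean change (19 df, critical value 2.093), from the noncentral t with noncentrality bias/SE

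Mid case: d = 0.05 L, and p = 0.75 on long-acting drugs × 0.50 dosing before the test = 0.375, with SD0 = 0.20 L.
- Bias = 0.05 × 0.375 = 0.019 L
- SD² = 0.0400 + 0.0025 × 0.375 × 0.625 = 0.0406, so SD = 0.2015 L and SE = 0.2015 / 4.472 = 0.0450 L
- Bias/SE = 0.42; coverage 0.932

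| d (L) | p | SD0 (L) | Bias (L) | Bias/SE | Coverage |
|---|---|---|---|---|---|
| 0 | any | any | 0 | 0 | 0.950 |
| any | 0 | any | 0 | 0 | 0.950 |
| 0.05 | 0.1875 | 0.20 | 0.009 | 0.21 | 0.945 |
| 0.05 | 0.375 | 0.20 | 0.019 | 0.42 | 0.932 |
| 0.05 | 0.75 | 0.20 | 0.038 | 0.83 | 0.876 |
| 0.10 | 0.25 | 0.25 | 0.025 | 0.44 | 0.930 |
| 0.10 | 0.50 | 0.25 | 0.050 | 0.88 | 0.867 |
| 0.10 | 1 | 0.15 | 0.100 | 2.98 | 0.19 |

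The last row is a bound, not an expectation. The protocol plans no such interval; coverage is only a way to scale the shift against the noise. With fewer than 20 completed pairs the SE is larger and bias/SE smaller, while the expected bias in litres is unchanged.

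**3. Reach.** None of the numbered items under Planned Analysis uses change in FEV1. FEV1 enters only item 15, as baseline severity, and that is unaffected. The primary PIF outcome and the at-risk rules come from device data and do not use clinic spirometry.

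**The case against.** **The asymmetry has a purpose.** The Spirometry paragraph ties washout to the pre-dose test, which is done only at visit 2, and follow-up without holds suits a real-world study and spares symptomatic patients. That explains the rule. It does not change the fact that the visit 2 post-dose test, the one carried forward for comparison, is done in the held state.

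**Albuterol levels the visits.** Every post-dose test follows the same four inhalations, which reduces the influence of earlier drugs. This stands as a reason to expect a small effect, possibly none. The documents give no figure for what remains.

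**The size is assumed.** This stands in full. The increment, the share dosing and the SD are not in the documents, and maintenance therapy is a recorded variable, not an entry criterion. If patients do hold the dose at visits 3 and 4, the shift is zero.

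**Timing is recorded, so analysis can help.** This stands in part. Patients who had not yet dosed are close to the visit 2 condition, those who had can be identified, and visit 3 to visit 4 is a comparison under one procedure. What cannot be supplied is a visit 2 value after a fresh maintenance dose, and subsets of 20 patients are small.

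**Stronger readings that the documents do not support.** A reader might take visit 2 for a drug-free baseline, but maintenance treatment continues through run-in and the hold is one dosing interval. A reader might also conclude that the primary objective is compromised, since it names reduced lung function as part of deterioration. No numbered analysis defines deterioration by change in FEV1, and the primary outcome is PIF.

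**Conclusion.** The concern holds as a minor design point. As written, the protocol compares a listed secondary outcome across unlike maintenance-drug states, and the washout line at visits 3 and 4 conflicts with the Testing section and has no rule behind it. Any resulting shift is toward improvement and arises only in patients who take a long-acting dose before the visit 3 or 4 test.

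The size is unknown. Under the assumed ranges the mean shift is 0 to 0.10 L, with a mid case of 0.019 L (0.42 SE), and near zero is plausible after albuterol. The direction follows from the visit procedures; the magnitude rests wholly on assumptions and should not be cited as a finding about this trial. It would go too far to call change in FEV1 uninterpretable: the study is declared exploratory, and the recorded dose times allow partial recovery.

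**What to change.** **For visits still to come.** Extend three existing rules to visits 3 and 4: the 12 h and 24 h hours for long-acting maintenance drugs (the LABA, LAMA and ICS-combination rows), the patient instruction given beforehand, and the reschedule rule. State that the maintenance dose is taken after post-bronchodilator testing. The 6 h hold of rescue SABA need not be added, because only post-albuterol tests are done at these visits. This also gives the washout review line a meaning.

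**If usual-care testing at visits 3 and 4 is intended.** Say so and delete washout from those two lists.

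**In that case, or for visits already run without the hold.** Use the recorded hours since the maintenance dose. Report change in FEV1 separately for patients who had and had not dosed before the test, and do not read the pooled change from visit 2 as disease change alone.

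**Cost.** The hold means visit-schedule wording, a delayed maintenance dose on two mornings in symptomatic patients, and some rescheduling, with no added test. The reporting route costs wording and a simple split of existing data.

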At the completion of at least 2 weeks of run-in (with a minimum of at least 8 rescue inhaler usages) and with documentation of stable clinical status throughout run-in, the patient will return for baseline testing; including vital signs, health related quality of life and Anthonisen Exacerbation questionnaires, pre and post bronchodilator spirometry and 6-minute walk testing (see table/flow chart). Average Peak Inspiratory Flow (Baseline PIF) and average Number of Rescue Inhalations per day (Baseline Inhalations) will be determined from the Digihaler Dashboard Data downloads during run-in.

In the event that the patient does not meet number of rescue inhaler usages or does not have a stable clinical status during run-in, an additional 2 weeks of run-in may be obtained. If at the end of the extended run-in period so that Baseline PIF and Baseline Inhalations cannot be determined or the patient continues to be clinically unstable, the patient will be discontinued from the study. If the patient has an upper respiratory tract infection or COPD exacerbation during run-in, they will also be discontinued from the study. Patients may be re-screened one time at a later date, when stable.

Once run-in and baseline testing are complete, all patients will continue on their maintenance COPD medications and use the ProAir Digihaler rescue SABA exclusively for the next 6 months. Patients will be provided with paper forms of the CAT, BCSS and Anthonisen Exacerbation criteria, to be completed at home on a weekly basis and mailed to the research center upon completion).

Throughout the treatment period, all rescue inhaler usage will be electronically transmitted to, monitored at and downloaded from the Digihaler Dashboard by the research center on every other business day basis (Monday, Wednesday and Friday). At the completion of each Digihaler Dashboard Data Download, comparisons of Daily PIF (average PIF of all rescue inhalations in a day) and Daily Inhalations (number of rescue inhalations in a day) to Baseline PIF and Baseline Inhalations will be made.

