If a serious adverse event occurs, the Institutional IRB will be notified within five business days of awareness of the event by the investigator. The study coordinator may initiate the IRB notification, but it must be filed by the study investigator or co-investigators. If the serious adverse event is fatal or life threatening, notification to the Institutional IRB must be made within 24 hours, irrespective of the extent of available adverse event information. This timeframe also applies to additional new information (follow-up) on previously forwarded serious adverse event reports.

The MedWatch 3500A form should be utilized to report serious adverse events to the FDA.

All adverse events (serious and non-serious) will be reported on the adverse event page(s) of the CRF. Adverse events should be reported using concise medical terminology on the CRFs. Non-serious AE's will be reported annually to the IRB as appropriate.

STATISTICAL ANALYSIS

Primary Outcome Measure:

- 1) Change in Peak Inspiratory Flow (PIF) from Baseline as measured via the ProAir Dihaler device

Secondary Outcome Measures:

1. Change in SABA use (Inhalations) from Baseline
2. Change in Inhalation Volume (IV) from Baseline
3. Change in CAT
4. Change in FEV₁

Other Outcome Measures:

1. Change in Anthonisen Exacerbation Criteria
2. Change in BCSS
3. Change in Inhalation Volume

All data is exploratory, with no calculated power or expected predictive probabilities. Statistical thresholds, comparisons, correlations and regressions, sensitivity/specificity/ROC analysis will be performed using Wizard 1.9.45 Statistics. Additional statistical analysis may be performed as per TEVA biostatistics.

PLANNED ANALYSIS

1. Average of PIF value and number of PIF events at 10%, 20%, 30%, 40% below Baseline PIF for 2 or more days per patient
2. Average summary statistics PIF values and frequency of PIF events across all patients
3. Number of inhalations per day that are 4 or more Inhalations above Baseline Inhalations for 2 or more days
4. Frequency of IV events that are 20% below Baseline (see Derived measurements) for 2 or more days
4. Frequency of combined events of PIF and IV 20% below Baseline and 4 or more Inhalations per day above Baseline for 2 or more days combined
5. Frequency of CAT events (defined as increase in CAT score by 2 above Baseline CAT score)
6. Correlation and regression analysis of PIF, Inhalations and IV events with CAT events

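### The planned correlation, regression and ROC analyses use repeated records from 20 patients but name no method that respects the patient as the unit

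*Protocol*

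**What the plan says.** The Protocol Overview plans "Twenty (20) patients with COPD requiring intermittent short acting beta agonist (SABA) rescue inhaler usage", followed for "a treatment period of 6 months and a follow-up period of 1 week". The CAT, BCSS and AEC forms are "to be completed at home on a weekly basis and mailed to the research center upon completion". Device data are reduced to daily values and compared with each patient's own baseline: "comparisons of Daily PIF (average PIF of all rescue inhalations in a day" and the daily inhalation count.

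STATISTICAL ANALYSIS names the methods and the software: "Statistical thresholds, comparisons, correlations and regressions, sensitivity/specificity/ROC analysis will be performed using Wizard 1.9.45 Statistics". PLANNED ANALYSIS then lists the associations. Item 6 is "Correlation and regression analysis of PIF, Inhalations and IV events with CAT events". Item 10 is "Correlation and regression analysis of PIF, Inhalations and IV events with AEC events", and item 11 does the same for BCSS. Item 7 varies the thresholds and durations. Items 12-14 correlate changes in PIF, SABA use and inhalation volume with changes in CAT.

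Items 1 and 2 are worded per patient and then across patients. Items 6-7 and 10-14 state no unit of analysis, and no item mentions repeated records. The section also says "All data is exploratory, with no calculated power or expected predictive probabilities" and leaves further analysis open to the sponsor's biostatistics group. It sets no significance level and no type of interval.

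**The concern.** The primary objective asks whether PIF trends go with deterioration, and the secondary objectives seek a threshold for use in practice. The at-risk rule compares each patient with that patient's own baseline. The question is therefore within-patient: does this patient's PIF fall, or SABA use rise, when this patient's CAT worsens?

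The named methods, in their plain form, can be applied to these data in two ways, and neither fits.

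- **Pooling all records** treats up to 520 patient-weeks as 520 separate observations and mixes within-patient with between-patient association.
- **One value per patient** respects independence, but it estimates only a between-patient association in 20 people.

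If records were pooled, a threshold with no within-patient signal could look well supported, and its sensitivity, specificity and AUC would be read with far more apparent data than 20 patients supply.

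**Working it through.** The protocol gives no power, alpha or interval figure to reproduce. The check asks what plain pooling would do.

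**Inputs from the protocol.** There are 20 patients, 6 months of treatment (taken as 26 weeks or 182 days), weekly forms and daily device values. That gives at most 20 × 26 = 520 weekly records and 20 × 182 = 3640 daily records. There are fewer for PIF and inhalation volume, which exist only on days with an inhalation.

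**Assumptions.** The test is two-sided at 5%. The ICC is varied because the protocol gives none, and it is taken as equal for both variables. Records within a patient are exchangeable, and there is no true association.

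**Formulas**, with m = 26 records per patient:

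- Correlation or slope: design effect DE = 1 + (m − 1) × ICC_x × ICC_y = 1 + 25 × ICC².
- Mean or proportion, such as pooled sensitivity: DE = 1 + 25 × ICC.
- Effective number = 520 / DE.
- Actual type I error of the pooled test of a correlation = 2 × (1 − Φ(1.96 / √DE)).

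| ICC | DE, correlation | Effective n | Type I, formula | Type I, simulated | Patient-centred, simulated | DE, proportion | Effective n |
|---|---|---|---|---|---|---|---|
| 0.1 | 1.25 | 416 | 8.0% | 8.4% | 5.5% | 3.5 | 149 |
| 0.3 | 3.25 | 160 | 27.7% | 27.1% | 4.8% | 8.5 | 61 |
| 0.5 | 7.25 | 72 | 46.7% | 46.4% | 4.7% | 13.5 | 39 |

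The weekly simulations used 4000 runs. For daily records (1500 runs), the pooled test rejects in about 23%, 61% and 76% of runs at the same ICCs.

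**Binary events.** Suppose patients differ only in event propensity, with assumed event rates of 15% and 30%. Pooled rejection is then 8%, 26% and 48% at ICC 0.1, 0.3 and 0.5. With heterogeneity set on the logit scale, it is 5.8%, 10.2% and 24.0% at a patient SD of 0.5, 1.0 and 1.5. Mild heterogeneity therefore does little harm.

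**Can own-baseline definitions remove the clustering?** Not entirely, because one baseline is subtracted from all of a patient's later values and its error is shared. Assume independent weekly values with variance 1 and no remaining patient effect.

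- PIF change from a two-week baseline mean: ICC = 0.5 / (1 + 0.5) = 1/3.
- CAT change from a single baseline reading (assumed): ICC = 1 / (1 + 1) = 1/2.
- DE = 1 + 25 × (1/3) × (1/2) = 5.17, so type I error = 2 × (1 − Φ(1.96 / 2.27)) ≈ 39%.

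Simulation gives 37.5% to 39% for the pooled correlation and 5.3% for the patient-centred one. For binary own-baseline events with illustrative cut-offs, the figures are about 21% and 4.1%.

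**One value per patient.** With n = 20, |r| must exceed 0.444 to reach p < 0.05, against 0.086 if 520 records are taken as independent. The test is valid, but it addresses the between-patient question.

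**The case against.** **The protocol never says that records are pooled.** A reader might infer from the list of methods that records will be analysed as if independent. The documents do not support that. One value per patient, a within-patient correlation or a mixed model all fit the wording, and items 1 and 2 point towards the patient. This objection stands, and it makes the concern conditional.

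**Repeated-measures handling is commonly left to the SAP, which is not shown.** This also stands: silence alone is not an error. The point rests on something narrower. The protocol commits to named methods whose plain versions, pooled or per patient, both miss its own objective.

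**Own-baseline definitions remove confounding by severity.** A reader might infer that sicker patients, with low PIF and high CAT, would produce a spurious link. That describes stable levels. PIF, inhalations, volume, CAT and BCSS are all analysed as changes or events against the patient's own baseline, which removes such differences. AEC events are the exception, since item 8 states no baseline. Differing event propensity and shared baseline error remain.

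**The size is not established.** Every ICC is assumed, and the weekly result runs from minor (8% at ICC 0.1) to large. The effective numbers 149, 61 and 39 belong to a mean or proportion; for a correlation they are 416, 160 and 72. A claim that results will be far too favourable goes beyond the documents.

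**The study is an exploratory pilot with no stated alpha.** No declared error rate is violated. That excuses the absence of power. It does not make an overstated precision acceptable when the intended product is a threshold for practice.

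**Conclusion.** The point holds in conditional form. For items 6-7 and 10-14 and the ROC analysis, the protocol names methods for heavily repeated data without one that respects the patient as the unit. If weekly records were pooled, a nominal 5% test of a correlation would reject about 8%, 27% and 46% of the time at ICC 0.1, 0.3 and 0.5, and the true standard error would be 1.1, 1.8 and 2.7 times the naive one. Shared baseline error alone could give about 39% under the equal-variance, single-CAT-baseline assumptions above. These figures rest on assumed ICCs, exchangeable records and complete weekly data. Nothing shows that the investigators will pool, and the unseen SAP may settle the matter. This is a cheap improvement to the plan, not a proven flaw in its results.

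**What to change.** Add a few sentences to PLANNED ANALYSIS:

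- The patient is the cluster in every association analysis.
- Items 12-14 use within-patient (repeated-measures) correlation.
- Items 6, 7, 10 and 11 use regression clustered by patient: a mixed model, or GEE with a small-sample correction because there are only 20 clusters.
- Intervals for sensitivity, specificity and AUC come from a bootstrap that resamples patients, not records.
- Within-patient and between-patient associations are reported separately.

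Other within-patient or clustered methods would also serve; what matters is that one is named. No new data or visits are needed, and the protocol already allows further analysis by the sponsor's biostatistics group. The cost is a little more programming and wider, less favourable intervals.
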